4.3. Study Duration

The overall duration of the patient enrollment, treatment and follow-up phase of the trial is expected to last 9 months.

The duration of an individual's participation, that completes the trial (Screening through the 3-month posttreatment LTFU visit) will be between 3.5 to 4.0 months depending on the length of time a participant is in the Screening Period (up to 4 weeks). [In rare cases, a participant's total duration of involvement could extend beyond 4.0 months if the Screening Period is extended and/or if it is deemed necessary to continue to monitor an adverse event that did not resolve prior to the date of the 3-month posttreatment LTFU visit.]

4.4. Study Endpoints

4.4.1 Primary Endpoints

Primary endpoints will be assessed using descriptive statistics. The statistical approaches are described Section 13.3 and will be detailed in the Statistical Analysis Plan (SAP) that will be developed and finalized before any analyses are undertaken.

- Number/Incidence of adverse events (AEs), and serious adverse events (SAEs) graded using the National Cancer Institute (NCI) Common Terminology Criteria for Adverse Events (CTCAE) version 5.0.
 - Number/Incidence of AE's related to clinically significant ECG/cardiac abnormalities

- Number/Incidence of AE's related to Heart Rate
 - Tachycardia (HR>100 bpm)
 - Bradycardia (HR < 50 bpm)
- Number/Incidence of AE's related to Blood Pressure
 - Hypotension
 - Hypertension
- Number/Incidence of AE's related to Liver Function
 - Liver function tests
- Number/Incidence of AE's related to Kidney Function
 - Renal function tests
- Number/Incidence of Mental and Psychotic AE's

4.4.2 Secondary Endpoints

Pharmacokinetic parameters will be estimated using standard methods; the statistical approaches are described in Section 13.4 and will be detailed in the Statistical Analysis Plan (SAP) that will be developed and finalized before any analyses are undertaken.

- PK parameters of psilocin including:
 - AUC_{0-t}
 - $AUC_{0-\infty}$
 - T_{max}
 - C_{max}
 - $t_{1/2}$

4.4.3 Exploratory Endpoints

Exploratory endpoints will be driven by a fundamental analysis of mean changes in clinician rating scales and patient QoL and PRO instruments compared from baseline to one or more visit timepoints. Mean changes in epigenetic markers also will be assessed. In addition, data captured by the health tracking wearable device will be assessed. For all exploratory endpoints, appropriate statistical methods will be employed as described, more generally in Section 13.5. A formal outline of the statistical methods to be employed will be detailed in the SAP.

- At Screening, participants will confirm that they have had a traumatic event, captured in the LEC-5 and that they have a minimum score of at least 33 as determined the PCL-5, respectively.
- Mean changes from baseline to various study visit timepoints (e.g., Study Day 7) will be calculated for the following instruments:
 - General Anxiety Disorder 7 Item Scale (GAD-7)
 - Patient Health Questionnaire-9 (PHQ -9)
 - Healing Experience of All Life Stressors (NIH HEALS)
 - Brief Pain Inventory (BPI)
 - Columbia-Suicide Severity Rating Scale (C-SSRS)

CONFIDENTIAL

- Profile of Mood States (POMS)
- Sheehan Disability Scale (SDS)
- Watts Connectedness Scale (WCS)
- Mystical Experience Questionnaire-revised (MEQ30)
- Challenging Experience Questionnaire (CEQ)
- 5-Dimensional Altered States of Consciousness Rating Scale (5D-ASC)
- Alcohol Use Disorders Identification Test (AUDIT)
- Drug Use Disorders Identification Test (DUDIT)
- Mean changes in epigenetic markers from baseline to various timepoints will be calculated for psychiatric and cardiovascular genes.
- Data collected by a health tracking wearable device such as nightly sleep duration, sleep latency, sleep efficiency, heart rate and heart rate variability during sleep, and daily steps will be calculated.

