
Exploratory Objectives:
 
 To evaluate the preliminary efficacy of psilocybin mushrooms. To assess changes in quality-of-life (QoL) after taking psilocybin mushrooms. To evaluate the impact of psilocybin mushrooms on objective sleep outcomes (sleep duration, sleep latency, sleep efficiency) via a health tracking wearable device. To evaluate the impact of psilocybin mushrooms on heart rate and heart rate variability (HRV) during sleep via a health tracking, wearable device. To evaluate the impact of psilocybin mushrooms on daily activity levels (i.e., steps) via a health tracking, wearable device. To assess mean changes in epigenetic markers of psychiatric- and cardiovascular-related genes. 	
Exploratory Endpoints:
 
 Generalized Anxiety Disorder 7 Item Scale (GAD-7) Life Events Checklist for DSM-5 (LEC-5) PTSD Checklist for DSM-5 (PCL-5) Patient Health Questionnaire-9 (PHQ -9) Healing Experience of All Life Stressors (NIH HEALS) Brief Pain Inventory (BPI) Columbia-Suicide Severity Rating Scale (C-SSRS) Profile of Mood States (POMS) Sheehan Disability Scale (SDS) Watts Connectedness Scale (WCS) Mystical Experience Questionnaire (MEQ30) – Revised Challenging Experience Questionnaire (CEQ) 5-Dimensional Altered States of Consciousness Rating Scale (5D-ASC) Alcohol Use Disorders Identification Test (AUDIT) Drug Use Disorders Identification Test (DUDIT) Nightly sleep duration, sleep latency, and sleep efficiency as measured via health tracking wearable device. Heart rate and heart rate variability during sleep as measured via a health tracking wearable device. Steps during daily activity as measured via a health tracking wearable device

Study Design:
 
This open-label Phase I trial will assess the safety, pharmacokinetics, and preliminary efficacy, of orally administered organic whole psilocybin-containing mushrooms among individuals with post-traumatic stress disorder (PTSD).
 
Up to 24 participants will be enrolled and treated with psilocybin mushrooms contained in a chocolate formulation. More detailed information on the required visit activities can be found in the SoE.
 
Prescreening:
 
Potential participants will provide verbal consent and be interviewed by phone to gauge their interest in and likelihood of qualifying for the trial.

Screening Period:

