2.2. Study Purpose

This open-label, Phase I study, will evaluate the safety, pharmacokinetics and preliminary efficacy of whole organic psilocybin mushrooms. This will be the first clinical trial testing the therapeutic potential of organic whole psilocybin mushrooms for patients with PTSD and will help determine the potential risks and benefits of using psilocybin as a treatment for PTSD. The results garnered from this trial can be used to inform the design of larger randomized controlled clinical trials.

The results also will provide physicians, patients, scientists, and regulators with critical knowledge regarding whether organic whole psilocybin mushrooms may have benefits in treating commonplace comorbidities of PTSD such as pain, anxiety and depression for individuals with PTSD, and the impact of this popular but untested regimen on clinical outcomes.

Individuals with PTSD that are to be included in this study will have satisfied the Diagnostic and Statistical Manual-5th edition (DSM-5) criteria for current PTSD with a duration of 6 months or longer, as assessed by a study psychiatrist.

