3.3. Exploratory Objectives

- To evaluate the preliminary efficacy of psilocybin mushrooms.
- To assess changes in quality of life after taking psilocybin mushrooms.
- To evaluate the impact of psilocybin mushrooms on objective sleep outcomes (sleep duration, sleep latency, sleep efficiency) via a health tracking wearable device.
- To evaluate the impact of psilocybin mushrooms on heart rate and heart rate variability (HRV) during sleep via a health tracking wearable device.
- To evaluate the impact of psilocybin mushrooms on daily activity levels (i.e., steps) via a health tracking wearable device.
- To evaluate mean changes in epigenetic markers of psychiatric- and cardiovascular-related genes.

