7.1.2 Pre-screening

Prospective participants may be interviewed by telephone to determine whether they might be suitable candidates to participate in the trial. At the start of the telephone interview, interviewees will provide verbal consent confirming that they are willing to share personally identifiable information and their personal health information to determine if they are likely to qualify for participation in the trial.

The pre-screening interview will include questions about the participant's medical and psychiatric history, current treatment, etc. The interviewees will be asked to provide responses to the 17-question Life Events Checklist for DSM-5 (LEC-5) and the 20-question PTSD Checklist for DSM-5 (PCL-5). Qualified study site staff will provide individuals that pass the pre-screening assessment with IRB-approved study information and consent materials for review and consideration.

- If the prospective participant is not eligible or not interested in taking part in the trial their personal information will be destroyed at, apart from the summary reason for ineligibility, which will be retained on the Screening Log. An eCRF will not be completed for candidates who are not enrolled.

Pre-screening information will be retained for candidates who provide specific permission via verbal consent for utilization and retention of this information and who and provide written informed consent to participate in the trial. The Screening Log will be completed to include the qualified participant's screening number. The Screening Log will be maintained and kept up-to-date and be available for review by the study site monitor.

Table 1

Schedule of Events

Activity	Pre-Screen	Screening Period		Day 1	Day 2	Day 4 (Virtual)	Day 8 (±1 day)	EoT Day 30 1 Month (±5 days)	LTFU 3 Month (±7 days)
		-30 - to -1 (Can be extended)							
			Prior to Study Day 1						
Pre-Screen Verbal Consent ¹	X								
LEC-5 [^]		X							
PCL-5 [^]		X							
Informed Consent		X							
Medical History	X	X		X	X	X	X	X	X
Concomitant Medications	X	X		X					
Eligibility Criteria	X	X		X					
Height / Weight ²		X					X	◆ ¹⁴	
Physical Exam ³		X					X	◆ ¹⁴	
Vital Signs ⁴		X		X	X		X	X	X
Urine Pregnancy Test ⁵		X							
Urine Drug / Alcohol Tests		X		X				X	X
Clinical Laboratory Tests ⁶		X ⁶		X			X	X	
Electrocardiogram ⁷		X		X			X		
Dispense/Collect Wearable		X						◆ ¹⁴	X
Saliva – Epigenetic Test				X			X	◆ ¹⁴	
Pharmacokinetic Test ⁸				X					
Administer Study Drug				X					

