7.1.3 Screening Period (Day -30 to -1)

If after the pre-screening telephone interview, the study site staff and/or the investigator feel the candidate may be suitable for the study, a Screening visit will be scheduled.

The initial Screening Visit will include the following protocol mandated activities, tests, examinations, assessments and procedures:

- Explain and obtain written informed consent from the candidate prior to performing any study-specific tests or evaluations.
- Issue a 3-digit screening number and record the appropriate information on the Screening Log.
- Review the participant's medical and psychological history including current and past medications and therapies.
 - Have the participant sign a medical release form to allow the Investigator to review his/her medical records to ensure the participant has no underlying medical conditions that would preclude their participation in the trial and confirm the PTSD diagnosis.
- Review the LEC and PCL-5 checklists.
- Review with female participants of childbearing potential their ability to become pregnant and commitment to practice appropriate birth control as defined in this protocol for the total duration of the study.
- The following clinician rating scales and participant QoL and PRO instruments should be administered and/or completed by the participant, respectively:
 - LEC-5 (at least one traumatic event causative for a diagnosis of PTSD)
 - PCL-5 (a score of at least 33)
 - GAD-7 (scores of ≥ 15 will exclude the participant)
 - PHQ-9 (scores of ≥ 20 will exclude the participant)
 - NIH HEALS
 - BPI
 - C-SSRS (category ratings of 4 or 5 will exclude the participant)
 - SDS
 - AUDIT
 - DUDIT
- Collect vital signs (blood pressure, pulse, body temperature, respiratory rate and pulse oximetry).
 - Perform a medical history directed physical examination. The examination will involve the following procedures:
 - Height/weight.
 - Examination of head, eyes, ears, nose, throat, skin, heart, lungs, abdomen and extremities.

CONFIDENTIAL

- Brief neurological exam (cranial nerves 2-12, sensory, motor, reflexes and cerebellar function).
- Obtain 12 lead ECG
- Collect urine for the following laboratory analyses:
 - Urine pregnancy test in women of childbearing potential.
 - Qualitative rapid urine drug screen.
 - Qualitative urine ethyl glucuronide (EtG) test to assess alcohol consumption.
- Collect a blood sample for clinical laboratory evaluations.

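### No PTSD symptom score is collected after dosing, although the synopsis lists the PCL-5 as an exploratory endpoint and the stated purpose includes benefit in PTSD

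*Protocol*

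**What the plan says.** The first exploratory objective in Section 3.3 reads "To evaluate the preliminary efficacy of psilocybin mushrooms". Section 2.2 says the trial "will help determine the potential risks and benefits of using psilocybin as a treatment for PTSD". It adds that the results will show whether the product "may have benefits in treating commonplace comorbidities of PTSD such as pain, anxiety and depression for individuals with PTSD". The protocol title names preliminary efficacy in patients with PTSD.

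The synopsis lists the PCL-5 as an exploratory endpoint. Section 4.1 (Screening Period) names the LEC-5 and PCL-5 among assessments that partly decide entry and partly set reference values for comparison before and after treatment.

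Section 4.4.3 gives the PCL-5 one role, at Screening, where participants must show that "they have a minimum score of at least 33 as determined the PCL-5". The sentence that opens the outcome list, "Mean changes from baseline to various study visit timepoints (e.g., Study Day 7) will be calculated for the following instruments", is followed by 13 instruments, and the PCL-5 is not one of them.

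On timing, Section 7.1.2 has candidates answer "the 20-question PTSD Checklist for DSM-5 (PCL-5") in the pre-screening phone interview. Section 7.1.3 repeats the scale at the Screening visit, again as a threshold: "PCL-5 (a score of at least 33"). Table 1 marks it in the Screening Period only, and its footnote describes an entry requirement.

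**The concern.** A scale listed as an endpoint needs at least one value after treatment. Section 12.5 plans to analyse change from baseline by visit for the continuous questionnaires, and for the PCL-5 there is nothing to subtract the baseline from. The missing data concern the condition under study. Worsening of PTSD symptoms would also have no scale-based measure, although psychiatric adverse events are still collected.

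This cannot be left to the SAP, because an SAP cannot analyse data that the protocol never collects. Nor can it be repaired later. Each participant is dosed once, and a Day 30 or Day 90 score not taken at the time is lost.

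**Working it through.** The protocol states no figure to reproduce: Section 12.2 justifies the 24 participants without a power calculation. The check is therefore a count of PCL-5 administrations, followed by the precision that the fix would give.

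**Step 1. Where the PCL-5 appears**

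| Time | Source | PCL-5 given? |
|---|---|---|
| Pre-screening phone interview | 7.1.2 text (not marked in Table 1) | Yes, before dosing |
| Screening visit | Table 1, 7.1.3 | Yes, before dosing |
| Day 1, pre-dose and post-dose | Tables 1 and 2, 7.1.4 | No |
| Day 2 | Table 1, 7.1.5 | No |
| Day 4 | Table 1, 7.1.6 | No |
| Day 8 | Table 1, 7.1.7 | No |
| Day 30/EoT | Table 1, 7.1.8 | No |
| 3-month LTFU | Table 1, 7.1.9 | No |

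There are at most two values before dosing and none after. The tables and the plain-text visit lists agree, so a damaged table does not explain the gap.

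**Step 2. Does another instrument fill the gap?** The LEC-5 records exposure to traumatic events. The DSM-5 diagnosis is made for entry. The 13 instruments in the change list cover anxiety, depression, healing, pain, suicidality, mood, disability, connectedness, acute drug experience, and alcohol and drug use. The remaining exploratory data are wearable measures and epigenetic markers. None is a PTSD severity score.

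**Step 3. Size of the gap.** Exhibit 3 asks about the past month, so the existing visits that roughly suit the form are Day 30 and Day 90.

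- Possible observations: 24 × 2 = 48. Planned: 0.
- At Day 8 most of the recall period would precede dosing, so that visit is not counted.
- Day 30 has a window of ±5 days. A visit on Day 25 is 24 days after Day 1, so with a 30-day month about 30 − 24 = 6 days of recall precede dosing. Day 90 (±7 days) has no such overlap.

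**Step 4. What the fix would deliver.** The 95% CI half-width for a mean paired change, in units of the SD of change, is t(0.975, n−1)/√n.

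- n = 24: 2.069/4.899 = 0.422
- n = 20: 2.093/4.472 = 0.468
- n = 18: 2.110/4.243 = 0.497

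The SD of PCL-5 change is not in the protocol. For an assumed SD of 12 to 18 points:

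- n = 24: 0.422 × 12 = 5.1 to 0.422 × 18 = 7.6 points
- n = 20: 0.468 × 12 = 5.6 to 0.468 × 18 = 8.4 points
- n = 18: 0.497 × 12 = 6.0 to 0.497 × 18 = 8.9 points

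The completer counts of 20 and 18 are illustrations, because the protocol gives no dropout assumption after dosing.

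**The case against.** The strongest reply is that this is a single-arm, open-label Phase I trial whose primary objective is safety and whose secondary objective is pharmacokinetics. Neither depends on a post-dose PCL-5, and an uncontrolled change could not establish efficacy. That is correct, and it limits the reach of the point. It does not explain why the synopsis lists an endpoint that cannot be computed.

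A second reply is that Section 4.4.3, Table 1 and the visit lists consistently treat the PCL-5 as a screening item, so the synopsis may be what is wrong. It also lists the LEC-5, which is plainly not an outcome. This has some force. But Section 4.1 places the PCL-5 among assessments that serve before-and-after comparison, and Section 2.2 speaks of treating PTSD itself. Deleting the PCL-5 from the synopsis would remove the contradiction and leave that purpose without a measure.

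Two stronger readings are tempting, and the documents support neither:

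- A reader might infer that preliminary efficacy cannot be addressed at all. The objective in Section 3.3 does not name PTSD symptoms, and Section 2.2 also names pain, anxiety and depression. Those are measured after dosing (BPI, GAD-7, PHQ-9), as is disability (SDS).
- A reader might infer that the trial cannot inform later randomized trials. Its safety, pharmacokinetic and comorbidity results can.

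**Conclusion.** The point holds in a specific form: as written, the trial cannot estimate change in PTSD symptoms for any participant at any visit, and cannot supply a PTSD effect or variance estimate for later trials. The gap is 0 of 48 possible observations, assuming 24 treated participants who all attend Day 30 and Day 90. The synopsis contradicts the schedule and Section 4.4.3, and the stated purpose of benefit in PTSD has no matching outcome.

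The precision figures describe what the fix would bring, not the defect. They rest on an assumed SD of change and on complete follow-up, and the interval widens with dropout. Even with the fix, the result would be an uncontrolled change, useful for planning and not as proof of effect.

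**What to change.** - Add the PCL-5 to Table 1 at Day 1 pre-dose, Day 30/EoT and the 3-month LTFU visit. Add it to Table 2 at pre-dose only, since that table covers Study Day 1 alone.
- Add it to the instrument lists in 7.1.4, 7.1.8 and 7.1.9, and to the change-from-baseline list in 4.4.3.
- State that the Day 1 pre-dose score is the baseline. Entry requires at least 33 at Screening, so change from that qualifying score would include regression to the mean. A separate Day 1 score reduces this but does not remove it, partly because its past-month recall can overlap that of Screening.
- Do not use the Exhibit 3 form at Day 8 unless wording with a shorter recall period is specified. State that an early Day 30 visit includes a few pre-dose days, and treat Day 90 as the clean past-month assessment.
- List the LEC-5 as an eligibility item, not an endpoint, in the synopsis.

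The cost is one 20-item self-report form at three existing visits, a small added burden for participants, and updates to the schedule, consent form and eCRF. No new visit, staff or participants are needed. The amendment has to be in force before the affected visits take place.
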